Title	Stellate Ganglion Block in Patients With Advanced Primary Parkinson' s Disease: a Small, Open, Randomized, Controlled Clinical Study
Bidders	Zhujiang Hospital of Southern Medical University
Leader of the unit	Zhujiang Hospital of Southern Medical University
Research purpose	
Main research purpose: To confirm that stellate ganglion block can improve motor symptoms in patients with Parkinson's disease.
 
Secondary research objectives: To determine the efficacy of stellate ganglion block in improving non-motor symptoms, activities of daily living and medication dosage in patients with primary Parkinson's disease.

Research hypothesis	Stellate ganglion block can improve motor and non-motor symptoms in patients with primary Parkinson's disease.
Study design	Single-center, randomized, open-label
Sample size	This study was a randomized controlled trial. The experimental group was treated with standard Parkinson's disease treatment + stellate ganglion block (SGB), and the control group was treated with standard Parkinson's disease treatment. According to the literature review and previous clinical observations, the standard deviation of the MDS-UPDRS scale score in the control group was 9.58 points, and the MDS-UPDRS-III score in the experimental group was expected to decrease by 10 points. 80%, and the loss to follow-up rate was 20%. According to the formula for calculating the sample size, 19 subjects were required to be studied in each of the experimental group and the control group, and at least 38 subjects were included in total.
Research object	
Diagnostic criteria: Parkinson's disease patients who met the 2016 MDS criteria for "probable PD" or "diagnosed PD"
 
Inclusion criteria:
 
 1. Age 45-80 years old; 2. Patients with Parkinson's disease who meet the diagnostic criteria of "probable PD" or "diagnosed PD" in MDS in 2016; 3. The patients or their legal guardians agree to participate in this trial and sign the informed consent form; 4. Hoehn-Yahr (H&Y) level 3 to 5; 
Exclusion criteria:

	
 1. Those who are allergic to local anesthetics; 2. Those who are unable to cooperate with sports or non-motor function monitoring; 3. Exclude patients with Parkinson's superimposed syndromes, such as corticobasal degeneration, dementia with Lewy bodies, multiple system atrophy, progressive supranuclear palsy; and secondary Parkinson's syndromes, such as vascular parkinsonism, drug poisons or patients with Parkinson's syndrome caused by trauma; 4. Refuse to sign the consent form.

Key Interventions
	
Experimental group: standard treatment of Parkinson's disease + SGB
 
Control group: standard treatment for Parkinson's disease

Follow-up
	
Intervention follow-up period: On Day0, Day5 and Day10 of the first, second and third cycles, the visiting schedule was used to record the required information. The interval of each cycle was 1 month, and the total follow-up time was 3 months.
 
Follow-up period: Modified MDS-UPDRS (Revised Movement Disorders Association Unified Parkinson's Disease Rating Scale) III scores were collected every month after treatment.

Evaluation index
	
Primary end point: MDS-UPDRS score.
 
Secondary end points: NMSS (Parkinson's disease Non-motor Symptom Evaluation Scale), PDQ-39 (39-item Parkinson's disease questionnaire), 10M-WT (walking speed test), H&Y grading (Hoehn Yahr (modified) Parkinson's disease grading), LDE (dopa equivalent dose).

Statistical method
	
SPSS25.0 software was used to analyze the data, and the measurement data were expressed by mean and standard deviation ($\bar{X} \pm S$). For those with normal distribution and homogeneity of variance, paired sample T test was used for intra-group comparison, two independent samples T test was used for inter-group comparison, and t 'test was used for those with uneven variance. The count data were expressed as percentage (%), and the chi-square test was used to compare the total effective rate between groups. $P < 0.05$ was considered as statistically significant difference.

Study time
	
Expected enrollment time of the first subject: 2022-01-01
 
Expected enrollment time of the last subject: 2022-06-30
 
Expected end time: 2024-06-30

Visit Schedule

	Screening stage	Intervention follow-up period			Observational follow-up period	Exit supervision
		Into the group	Follow-up 1	Follow-up 2	Follow-up 3	
Supervision stage	V _S	V ₁	V ₂	V ₃	V ₄	
Supervision time	-1day	0	4weeks ±3	8weeks ±3	12weeks±3	
Informed consent	*					
Main evaluation indicators (MDS-UPDRS)	*		*	*	*	when necessary
Secondary evaluation indicators (NMSS、PDQ-39、10M-WT、H&Y、LDE)	*		*	*	*	when necessary
Demographic information^A	*					
Medical history^B	*					
Vital signs^C	*		*	*	*	*
Physical examination^D	*		*	*	*	*

Laboratory tests (hematology/biochemistry/urinalysis)^E	*		*	*	*	必要时
Blood biomarkers^F	*				*	
Film degree exam^G	*				*	
Previous/concomitant medications^H	*					
Adverse event	*	*	*	*	*	*

Remark:

A. Demographics will include the subject's date of birth, gender, ethnicity, education, marriage, occupational information;

B. Medical history includes comorbid diseases and other clinically significant past medical history, medication history, and surgical trauma history;

C. Vital signs will include blood pressure, pulse rate, respiration and temperature;

D. Physical examination includes medical physical examination and neurology specialist physical examination;

E. Clinical laboratory examination: blood routine, serum biochemistry, coagulation, ceruloplasmin, gene expression level;

F. Blood biomarkers: IL-2, APEO, α -synuclein, DJ-1 protein, etc.;

G. Imaging examination: MRA, SWI;

H. The type, dose, and time of previously used drugs.

1. Research background

Parkinson's disease (PD) is a relatively common degenerative disease of the central nervous system, and China's population has grown significantly over the past few decades, resulting in a rapid increase in the number of elderly people; 2016 Global Burden of Disease Study Report It is said that the number of PD patients in China accounts for about 23% of the total PD population in the world^[1]; by the end of 2020, it is estimated that the number of people with Parkinson's in China will be about 3.62 million, and it is estimated that by 2030, 50% of PD patients in the world will be Chinese^[2]. Parkinson's disease is mainly manifested by motor symptoms such as bradykinesia, rigidity, and tremor, as well as non-motor symptoms such as autonomic dysfunction, sleep disturbance, and hyposmia^[1].

Both motor symptoms and non-motor symptoms can significantly affect the quality of life of patients^[3]. At present, drug treatment represented by dopa is still the first choice for Parkinson's treatment guidelines at home and abroad. However, in the middle and late stages of the disease, side effects such as symptom fluctuations or dyskinesia complicated by long-term medication gradually appear, and the efficacy of levodopa in patients declines^[4-5], seriously affecting the quality of life of patients. For patients with advanced Parkinson's disease, the current anti-parkinsonian guidelines advocate drug therapy combined with non-drug therapy for comprehensive treatment. Deep brain stimulation (DBS), as the main non-drug method for Parkinson's treatment, has limited its wide clinical application due to its complicated operation, invasiveness, high cost and many side effects^[6-7]. Functional exercises limited to a certain aspect such as language and swallowing have limited efficacy^[8-9], so it is imperative to find new treatments for Parkinson's disease.

Stellate ganglion block (SGB) is a commonly used sympathetic nerve regulation method in clinic. It can treat and protect various CNS diseases by regulating inflammatory response, oxidative stress level and immune endocrine function. role^[10]. The mechanism of action of SGB can be divided into the central action mechanism and the peripheral action mechanism. The central action maintains the stability of the internal environment by regulating the hypothalamus, so as to keep the body's endocrine function, autonomic function and immune function normal^[11]. It has curative effects on inflammation and pain relief, reducing free radicals, inhibiting neuronal apoptosis, improving cognitive function, regulating cerebral oxygen metabolism, regulating sleep, and dilating blood vessels. SGB can inhibit the occurrence and maintenance of mechanical hyperalgesia in PD rats by reducing inflammatory cytokines in the striatum and PAG^[10]. SGB can reduce the production of free radicals, reduce the levels of serum β -amyloid (A β)-42, phosphorylated Tau-181 protein and IL-6, and reduce the expression of abnormal phosphorylation of Tau protein to protect neuronal cells^[12]; It may improve cognitive function by down-regulating hippocampal neuronal adenylate-activated protein kinase (AMPK) and inhibiting astrocyte activation^[13]; the right SGB may alleviate the MT effect by reducing excessive hippocampal inflammatory response and neuronal apoptosis. It can effectively alleviate spatial learning and memory dysfunction^[14], and restore various biological rhythms by correcting melatonin rhythm^[15]. Uchida et al also believed that SGB can reduce sympathetic nervous tension, thereby regulating sleep^[16]. SGB can increase blood flow, make the anterior, middle and posterior cerebral arteries, vertebral arteries, carotid arteries, brachial arteries, blood flow velocity, blood flow, and blood vessel diameters all increased, vascular resistance decreased, and the diameter of small arteries increased more significantly^[17], stimulates the olfactory nerve by increasing blood flow, which improves the olfactory dysfunction for a long time^[18]. SGB may inhibit the secondary apoptosis of injured neurons by promoting the conduction of anti-apoptotic signaling pathways; regulating the levels of lymphocyte NF- κ

B protein, IL-1 β and TNF- α , and CGRP through the neuro-endocrine-immune system; and It has neuroendocrine regulating effect: can regulate calcitonin, NO, endothelin, serum adrenocorticotrophic hormone (ACTH), α -melanocyte stimulating hormone (MSH) and β -endorphin (β measurement end), etc^[19]; Parkinson's patients have neuro-endocrine-immune system dysfunction. When we used SGB to treat dizziness in PD patients in our previous clinical practice, we unexpectedly found that SGB significantly improved the patients' motor and non-motor symptoms.

At present, there are no reports on the application of SGB in the treatment of Parkinson's patients at home and abroad. Based on the previous clinical observation, this topic intends to use SGB to treat patients with advanced Parkinson's disease through an open, randomized controlled small-sample clinical study, so as to clarify the ability of SGB to treat patients with Parkinson's disease. Effectively improve motor symptoms and non-motor symptoms in patients with advanced Parkinson's disease.

2. Research purpose

Main research purpose: To confirm that stellate ganglion block can improve motor symptoms in patients with Parkinson's disease.

Secondary research objectives: To determine the efficacy of stellate ganglion block in improving non-motor symptoms, activities of daily living and medication dosage in patients with primary Parkinson's disease.

3. Research hypothesis

Stellate ganglion block can improve motor and non-motor symptoms in patients with Parkinson's disease.

4. Study Design

4.1 Type of design and duration of follow-up

This study is a randomized controlled, open-label clinical study initiated by Zhujiang Hospital of Southern Medical University, with a follow-up period of 6 months.

4.2 Grouping method and blinding level

Grouping: The study was divided into an experimental group (standard antiparkinsonian therapy + SGB) and a control group (standard antiparkinsonian therapy).

Random: Use a stratified randomization method. Group study subjects by age. After grouping, there will be 2 subgroups: ① patients aged 45-60 years, ② patients aged 61-80 years. The 2 subgroups were divided into the experimental group and the control group according to 1:1, and finally the experimental group and the control group in the 2 subgroups were pooled.

Open: Both investigators and patients were aware of the grouping of patients.

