4.3 Sample size calculation

This clinical trial adopts the sample size calculation formula of 2 groups of quantitative data.

$$n = \frac{(Z_{\alpha} + Z_{\beta})^2 * 2\sigma^2}{\delta^2}$$

Calculation formula:

n represents the sample size of each group.

Take α as 0.05, Z value as two-sided, $Z_{\alpha} = 1.96$; β as one-sided, take power (test power) as 0.8, $Z_{\beta} = 0.84$.

σ represents the difference between the standard deviations of the treatment group and the control group, which is about 9.58 according to previous observations; δ represents the difference of the mean, that is, the difference between the mean of the treatment group and the control group, which is 10; the loss to follow-up rate is 20%.

According to the formula for calculating the sample size, there were 19 subjects in each of the experimental group and the control group, and a total of 38 subjects were included.

5. Subject recruitment

A total of 38 middle-advanced primary PD patients and controls who met the requirements in the inpatient or outpatient department of neurology of Zhujiang Hospital were continuously recruited.

6. Research subjects

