6.2 Standard constrain

- (1) Age 45-80 years old;
- (2) Parkinson's disease patients who meet the 2016 MDS "probable PD" or "diagnosed PD" diagnostic criteria;
- (3) Patients or their legal guardians agreed to participate in this trial and signed the informed consent form;
- (4) Hoehn-Yahr (H&Y) grades 3 to 5;

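### Chance imbalance in disease stage goes uncorrected: 38 patients at H&Y 3 to 5 are stratified by age alone, and the primary between-arm test is unadjusted

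*Protocol*

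**What the plan says.** - **Randomisation (Protocol 4.2).** Age is the only factor: "Use a stratified randomization method. Group study subjects by age. After grouping, there will be 2 subgroups", namely 45-60 and 61-80 years. Allocation is equal within each band: "The 2 subgroups were divided into the experimental group and the control group according to 1:1". The arms are then pooled across bands. Section 8.2 repeats that randomisation is stratified and adds no factor.
- **Population (6.2 and 5).** Entry requires "Hoehn-Yahr (H&Y) grades 3 to 5". Section 5 describes the sample as "A total of 38 middle-advanced primary PD patients and controls".
- **Timing (visit schedule, 8.1, 8.2).** H&Y and MDS-UPDRS are both scored at screening, the day before randomisation on Day 0.
- **Primary endpoint (10.1).** The MDS-UPDRS score, whose parts include motor symptoms and activities of daily living.
- **Primary analysis.** The synopsis (Statistical method) states "two independent samples T test was used for inter-group comparison", and 13.2.6 repeats this for the primary endpoint, with the unequal-variance version where needed. No covariate is named. Section 13.2.5 only describes baseline data.
- **Planning figures (4.3).** SD 9.58, difference 10 points, "Take α as 0.05, Z value as two-sided", "take power (test power) as 0.8", 20% loss to follow-up, 19 per arm.

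**The concern.** H&Y grade and MDS-UPDRS both measure the severity of the same disease, so patients at H&Y 4-5 should tend to score worse than patients at H&Y 3. The protocol does not say how strongly the two are linked, but the motor and daily-living content of the scale makes some link very likely. Stage is known before allocation, yet it is used neither in the randomisation nor in the primary comparison.

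In a trial of 38 patients, one arm can by chance receive noticeably more H&Y 4-5 patients. With an unadjusted comparison, that difference passes straight into the estimated treatment effect. A reader of the baseline table would see the imbalance and could not tell how much of the result it explains. Precision that the screening data could provide is also left unused.

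**Working it through.** **1. The protocol's own sample size.** From 4.3: (1.96 + 0.84)² × 2 × 9.58² / 10² = 14.39, so 15 per arm. Allowing for 20% loss, 15 / 0.8 = 18.75, so 19 per arm and 38 in total. The stated figure reproduces.

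**2. Chance of a stage imbalance.** Assumptions: K of the 38 patients are H&Y 4-5, stage is unrelated to age band, and each arm has 19. The number of H&Y 4-5 patients in one arm is then hypergeometric (38, K, 19). The protocol gives no stage mix, so K runs from 13 to 19.

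| K at H&Y 4-5 | P(arms differ by 5 or more) |
|---|---|
| 13 | 17.0% |
| 14 | 9.1% |
| 15 | 18.4% |
| 16 | 9.9% |
| 17 | 19.1% |
| 18 | 10.3% |
| 19 | 19.4% |

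The alternation is a parity effect. If K is even, the difference between arms is even, so 5 or more means 6 or more. The range is 9% to 19%. Outside it, with only 8 of 38 at H&Y 4-5, the figure is 4.2%.

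**3. Effect on the arm difference.** If mean score levels differ by G points between H&Y 3 and H&Y 4-5, a 5-patient difference shifts the arm difference by (5/19) × G. The protocol gives no value for G, so it is assumed:
- G = 5: 5/19 × 5 = 1.3 points.
- G = 10: 5/19 × 10 = 2.6 points, or 26% of the planned 10.

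This holds when score levels are compared. If change from baseline is compared, the gap in level largely cancels, and what remains depends on how far stage predicts change.

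**4. Precision available from modelling stage.** Take 9.58 as the total SD of the compared score, 15 evaluable patients per arm and an even stage split. An even split with gap G contributes 0.25 × G² to the variance.
- Stage ignored: SE = 9.58 × √(2/15) = 3.50.
- Stage modelled, G = 5: 3.50 × √(1 − 0.25 × 25 / 91.78) = 3.50 × 0.965 = 3.38, about 3% smaller.
- Stage modelled, G = 10: 3.50 × √(1 − 0.25 × 100 / 91.78) = 3.50 × 0.853 = 2.98, about 15% smaller.

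These figures take stage as balanced between the arms. A chance imbalance and the few degrees of freedom spent on covariates reduce the gain slightly.

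**The case against.** **Stratifying 38 patients by one two-level factor is a valid design, and a protocol need not defend its choice of age.** This stands. Nothing in 4.2 is an error or a contradiction. The point concerns the combination of that choice with an unadjusted comparison.

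**Chance imbalance is ordinary sampling error.** This also stands. A reader might infer that the age-only scheme biases the trial or inflates the type I error. It does neither: randomisation is valid, and the t-test's standard error already allows for chance imbalance. What is lost is precision, and confidence in the single result obtained.

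**Covariates are commonly left to a SAP.** That would answer a silent protocol, but 13.2.6 is not silent. It names the primary between-arm test, and that test has no covariate.

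**The planned effect may be a change.** The synopsis speaks of the MDS-UPDRS-III score in the experimental group decreasing by 10 points. If change is what is compared, the shift in step 3 is smaller. But 13.2.6 names the scale score and does not say that change is compared between arms, so the protection is not secured.

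**The most severe patients may be few.** Section 6.3 excludes those who cannot cooperate with monitoring, which may limit H&Y 5. This could narrow the stage mix, but H&Y 3 to 5 remains the stated range.

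**Stratifying by stage would not by itself shrink the reported standard error.** Correct. The gain in step 4 comes mainly from modelling, which is why the fix is aimed at the analysis.

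**Conclusion.** The point holds as a weakness in precision and credibility that can be repaired cheaply. Under the assumed stage mix, the arms would differ by 5 or more H&Y 4-5 patients with a probability of 9% to 19%: about 9-10% for even counts and 17-19% for odd counts. With an assumed 10-point stage gap in score level, such a difference is worth about 2.6 of the planned 10 points. Modelling stage would cut the standard error by about 3% or 15% for assumed stage gaps of 5 or 10 points. The stage mix, the stage gap and the reading of 9.58 as the SD of the compared score are all assumptions; the documents give only the last of these figures.

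Two stronger readings are not supported. One could reach a standard-error reduction of 38% by assuming a 15-point gap, but then stage would explain 0.25 × 225 / 91.78 = 61% of the variance, and nothing in the protocol suggests so tight a link. One might also conclude that age is the wrong factor and must be replaced. No figure in the protocol ranks age against stage, so that choice remains a trade-off.

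**What to change.** In 13.2.6 (and in the matching synopsis text), replace the unadjusted t-test for the primary between-arm comparison by a linear model (ANCOVA) with treatment and the following screening covariates:
- H&Y grade, 3 versus 4-5;
- the age stratum used in randomisation;
- preferably, the screening MDS-UPDRS score, for the same part or total as the outcome.

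Fix the model before outcome data are compared by arm. The cost is a few sentences and up to three residual degrees of freedom, out of 28 with 15 evaluable patients per arm. No extra patients, visits or measurements are needed, and the sample size stays at 19 per arm.

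Optional, and only if the randomisation list is not yet in use: consider H&Y (3 versus 4-5) as a stratification factor in 4.2 and 8.2. Replacing age gives up enforced age balance. Keeping both gives four strata averaging 9 to 10 patients, which needs small blocks. Either is defensible, and neither is required once the analysis is adjusted.

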4.3 Sample size calculation

This clinical trial adopts the sample size calculation formula of 2 groups of quantitative data.

$$n = \frac{(Z_{\alpha} + Z_{\beta})^2 * 2\sigma^2}{\delta^2}$$

Calculation formula:

n represents the sample size of each group.

Take α as 0.05, Z value as two-sided, $Z_{\alpha} = 1.96$; β as one-sided, take power (test power) as 0.8, $Z_{\beta} = 0.84$.

σ represents the difference between the standard deviations of the treatment group and the control group, which is about 9.58 according to previous observations; δ represents the difference of the mean, that is, the difference between the mean of the treatment group and the control group, which is 10; the loss to follow-up rate is 20%.

According to the formula for calculating the sample size, there were 19 subjects in each of the experimental group and the control group, and a total of 38 subjects were included.

5. Subject recruitment

A total of 38 middle-advanced primary PD patients and controls who met the requirements in the inpatient or outpatient department of neurology of Zhujiang Hospital were continuously recruited.

6. Research subjects

6.1 Diagnostic criteria

Parkinson's disease patients who met the 2016 MDS criteria for "probable PD" or "confirmed PD".

6.2 Standard constrain

- (1) Age 45-80 years old;
- (2) Parkinson's disease patients who meet the 2016 MDS "probable PD" or "diagnosed PD" diagnostic criteria;
- (3) Patients or their legal guardians agreed to participate in this trial and signed the informed consent form;
- (4) Hoehn-Yahr (H&Y) grades 3 to 5;

6.3 Exclusion criteria

- (1) Allergic to local anesthetics;
- (2) Those who cannot cooperate with exercise and non-exercise monitoring;
- (3) Exclude Parkinsonian-plus syndromes, such as corticobasal degeneration, dementia with Lewy bodies, multiple system atrophy, progressive supranuclear palsy; and secondary parkinsonism, such as vascular parkinsonism, drug toxicity, or trauma Patients with Parkinson's syndrome caused by;
- (4) Those who refused to sign the informed consent form.

6.4 Exit criteria

- (1) Subjects should withdraw from the trial when they have abnormal vital organ function, allergic reactions to drugs, poor compliance, exacerbation of the disease, or serious adverse reactions that need to stop the treatment of the trial drug or use other treatment methods;
- (2) Subjects who are ineffective, cannot tolerate adverse reactions, wish to take other treatment methods, or request to withdraw from the trial without any reason.

7. Research Interventions

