9.1 Withdrawal Criteria

Reasons for a subject to withdraw from the study may include:

Subjects should withdraw from the trial when they have abnormal vital organ function, allergic reactions to drugs, poor compliance, exacerbation of disease or serious adverse reactions that require stopping the treatment of the trial drug or using other treatment methods;

Subjects who are ineffective, cannot tolerate adverse reactions, wish to take other treatment methods, or request to withdraw from the trial without any reason.

Subject withdrew informed consent and refused further follow-up;

Subjects lost to follow-up;

Subject died.

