13.1 Statistical Analysis Data Set Definition

① Intentional analysis set (Intention-to-treat population)

All subjects who participated in randomization were included.

② Full analysis set (Full Analysis Set)

According to the principle of intention-to-treat analysis (ITT), all subjects who were randomized and who had received at least one post-treatment efficacy assessment were included.

③ Compliant with the scheme set (Per-protocol Set)

All patients who met the trial protocol, had good compliance (80%-120% of medication), did not use prohibited medication during the trial or completed the contents of the case report form.

④ Security Analysis Set (Safety Analysis Set)

All enrolled cases, all patients who have used the trial drug at least once and have safety records after drug use, belong to the safety analysis set. This dataset is used for safety analysis.

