13.2.3 Missing data imputation

If the patient fails to complete the corresponding scale or CRF due to force majeure factors, it should be completed within one week of missing data; if the patient withdraws from the study or terminates the study treatment, the corresponding missing data need not be completed.

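### Poor compliance ends trial participation (6.4, 9.1) and 13.2.3 waives the later scores, so randomised non-compliers may have no later MDS-UPDRS data; the bias could go either way

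*Protocol*

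**What the plan says.** Section 6.4(1) lists who is to leave the trial: "Subjects should withdraw from the trial when they have abnormal vital organ function, allergic reactions to drugs, poor compliance", followed by worsening and serious reactions. Section 9.1 repeats the list as reasons for withdrawal from the study: "allergic reactions to drugs, poor compliance, exacerbation of disease or serious adverse reactions that require stopping the treatment of the trial drug". Section 6.4(2) adds further exits linked to outcome: "Subjects who are ineffective, cannot tolerate adverse reactions, wish to take other treatment methods". Section 9.2 is a separate list for stopping study treatment, and it does not name poor compliance.

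On data after such an exit, section 13.2.3 states: "if the patient withdraws from the study or terminates the study treatment, the corresponding missing data need not be completed". It gives no imputation rule. Section 9.3 asks for a final efficacy and safety check at withdrawal, but the visit schedule has MDS-UPDRS at exit only if it is judged necessary.

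Section 13.1 defines the intention-to-treat set as follows: "All subjects who participated in randomization were included". The full analysis set requires one score after treatment: "all subjects who were randomized and who had received at least one post-treatment efficacy assessment were included". Compliance enters only in the per-protocol set: "All patients who met the trial protocol, had good compliance (80%-120% of medication". Section 13.2.6 plans a two-sample t-test for the primary endpoint and does not tie it to any of these sets.

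**The concern.** An intention-to-treat set is useful only if the patients in it have outcomes. Here the protocol's own rules take non-compliers out of the trial and then waive their later scores. They still count as randomised, but a t-test at week 8 or week 12 cannot use a patient who has no score at that visit.

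The two arms do not face the same demands. Both take oral drugs, but only the block arm has repeated daily procedures: 30 under section 7.2 (3 cycles of 10), or 18 to 30 under section 10.1 (3 cycles of 6 to 10 days). Those two passages need to be reconciled in their own right. Section 6.4 gives no threshold for poor compliance, and section 4.2 has investigators and patients aware of allocation, so the exit is an unblinded judgement. Different withdrawal in the two arms is therefore plausible. If withdrawn patients also differ in outcome from those who stay, the later comparison is no longer the randomised one. No analysis plan written afterwards can recover scores that were never collected.

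**Working it through.** **1. The plan's own figure.** Section 4.3 gives σ = 9.58, δ = 10, Zα = 1.96, Zβ = 0.84 and 20% loss.

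n = (1.96 + 0.84)² × 2 × 9.58² / 10² = 14.39, rounded up to 15. Then 15 / (1 − 0.20) = 18.75, rounded up to 19 per arm, 38 in total. The stated figure reproduces.

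**2. A non-complier followed through the rules.**
- Sections 6.4(1) and 9.1: the patient leaves the trial.
- Section 9.3 and the visit schedule: at most one exit score, and MDS-UPDRS is optional at that point.
- Section 13.2.3: the remaining scores need not be completed.
- Section 13.1: the patient stays in the intention-to-treat set, and in the full analysis set if any post-treatment score exists.
- Section 13.2.6: the t-test at a later visit has no value for this patient.

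**3. Size and direction of the bias.** In one arm, let a share d be withdrawn, and let those patients do g points worse than the retained mean m (improvement scale). The mean of all randomised patients is (1 − d)m + d(m − g) = m − dg, so using only retained patients overstates that arm by dg. The between-arm difference is then shifted towards the block by

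bias = d_block × g_block − d_control × g_control.

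The documents give neither d by arm nor g. The values below are assumptions, with d held within the plan's 20% loss allowance.

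| d block | d control | g block | g control | bias towards block (points) |
|---|---|---|---|---|
| 20% | 0% | 5 | 5 | 0.20×5 − 0 = +1.0 |
| 20% | 20% | 5 | 5 | 1.0 − 1.0 = 0 |
| 0% | 20% | 5 | 5 | 0 − 1.0 = −1.0 |
| 20% | 0% | 10 | 10 | +2.0 |
| 0% | 20% | 10 | 10 | −2.0 |
| 20% | 20% | 0 | 5 | 0 − 1.0 = −1.0 |
| 20% | 20% | 5 | 0 | 1.0 − 0 = +1.0 |

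**4. Scale.** With 19 patients in one arm and 19 × 0.8 = 15.2 in the other, SE = 9.58 × √(1/19 + 1/15.2) = 3.30. A shift of 1 point is 0.30 SE and 10% of the planned 10-point effect. A shift of 2 points is 0.61 SE and 20%.

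**5. What the 20% allowance covers.** By the normal approximation, power at δ = 10 and σ = 9.58 is 89.6% with 19 per arm and 81.6% with 15 per arm. The allowance protects power against lost numbers. It does nothing about who is lost.

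**The case against.** Several points on the other side are sound.

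**No contradiction inside 13.1.** A reader might infer that 6.4 and 13.1 give opposing rules. They do not: a withdrawn non-complier can be in the intention-to-treat set and outside the per-protocol set. The conflict is between trial exit combined with 13.2.3 and the intention-to-treat principle.

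**Not a compliers-only analysis.** A reader might also infer that the primary comparison becomes one of compliers only. That goes too far. Section 10.1 schedules scores within each cycle, 9.3 calls for an efficacy check at exit, and the primary test is not tied to the per-protocol set. Section 13.2.3 waives later data but does not forbid collecting it. What remains is a risk at later visits, because one early exit score is not a week-12 outcome.

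**No fixed direction.** The heavier schedule makes it tempting to say that the block arm is favoured. But the exit rule covers both arms, no compliance or dropout rate by arm is given, the only stated compliance measure concerns medication, which both arms take, and patients may be inpatients.

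A one-sided scenario shows how much such a claim assumes. Let all controls stay, let q = 10% to 20% of block patients be non-compliant, let them keep a share s = 0 to 50% of the effect, and let them score 0 to 4.79 points (0.5 SD) worse. With everyone kept, the difference is 10 × (1 − q(1 − s)) = 8.0 to 9.5. With non-compliers removed it is 10 + q × (0 to 4.79) = 10.0 to 10.96. The gap is 0.5 to 2.96 points, but it comprises 0.5 to 2.0 points of effect dilution and 0 to 0.96 of prognostic selection, and no input could make it negative. It is not an estimate of the bias.

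**Narrower reading of 6.4.** In the translated sentence, the clause about needing to stop the trial drug may qualify the whole list. If so, fewer patients leave for poor compliance, but 13.2.3 waives data after stopping treatment as well, so the gap in the data remains.

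**Left to the SAP.** The analysis set for the primary test and the handling of missing scores may be settled there. The instruction not to pursue the scores is in the protocol.

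**Conclusion.** The point holds in this form: trial exit for poor compliance, together with the waiver in 13.2.3, can leave randomised patients without later MDS-UPDRS scores and so bias the primary comparison at later visits. The cause is a stated rule and not an omitted detail.

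Under the assumed values the shift is about 1 point in either direction for a 5-point gap and 2 points for a 10-point gap, when 20% are withdrawn in one arm and none in the other. It is 0 when both share and gap are equal. These figures rest on assumed withdrawal shares and outcome gaps. The documents establish the mechanism, not its size or sign. The change is one that should be made, mainly because it is cheap now and the data cannot be recovered later.

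**What to change.** Separate stopping study treatment from leaving the trial, for follow-up and analysis purposes.

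- **Sections 6.4 and 9.1:** state that poor compliance alone does not end follow-up. It is recorded and leads only to exclusion from the per-protocol set, in line with 13.1.
- **Section 13.2.3:** state that MDS-UPDRS at V2 to V4 is still collected, and the patient analysed as randomised, after non-compliance or treatment discontinuation, unless consent is withdrawn. Amending 6.4 and 9.1 alone would not be enough, because 13.2.3 also waives the data of a patient who merely stops treatment.
- **Section 9.3 and the visit schedule:** reconcile the required efficacy check at withdrawal with the optional MDS-UPDRS entry at exit.

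Decisions on treatment stay with the investigator, and the right to withdraw consent is unchanged. The cost is a wording amendment and minor effort to follow patients who have stopped treatment. The visits are already scheduled and no patients are added. The downside is that keeping non-compliers dilutes the expected effect somewhat.
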